## SECTION A

### INTRODUCTION

Resident well-being remains a persistent, concerning issue. Throughout the course of residency, trainees experience significant stressors, including heavy workloads, adverse patient events, an increasingly complex body of knowledge to master, and limited time with family and support structures. Subject to a power differential, they also are susceptible to mistreatment, such as discrimination, harassment, and abuse. This combination of stressors and/or mistreatment results in potentially “toxic” learning environments that negatively impact well-being, leading to adverse outcomes such as burnout, attrition, and suicide.

Through a six-year partnership with the Accreditation Council Graduate Medical Education (ACGME), the American College of Surgeons (ACS), the American Board of Surgery (ABS), and the Association of Program Directors in Surgery (APDS), our team created the largest consortium of general surgery programs in the country (N=121) in order to conduct the Flexibility In duty hour Requirements for Surgical Trainees (FIRST) Trial ([www.TheFirstTrial.org](http://www.TheFirstTrial.org)). This work spurred national policy change for residents across all specialties through the ACGME 2017 Common Program Requirements revisions. As part of FIRST Trial follow-up, we administer an annual survey in conjunction with the ABS In-Training Examination (ABSITE), which is taken by all residents training in U.S. ACGME-accredited general surgery programs. This survey achieves an unparalleled 99% response rate, thus avoiding the non-response bias of nearly every prior study. Thus, we were uniquely able to quantify surgical resident well-being: 39% of all surgical residents experience weekly burnout symptoms, 12.6% think of leaving their programs, and 4.5% admit to suicidal thoughts.

To further understand the survey findings, our research team conducted annual interviews and focus groups with residents, faculty, and program directors across the country. This qualitative work highlighted two critical issues impeding programs’ abilities to address issues with their learning environments and/or their residents’ well-being: (1) Programs are unable to self-assess; although they recognize the importance of the learning environment and their residents’ well-being, they lack the means to objectively measure their performance in these domains. Standard instruments exist for only a narrow range of relevant environmental exposures and/or well-being outcomes. Programs with the initiative and resources to identify and administer appropriate instruments subsequently struggle with interpretation. Published data exist only for small subsets of residents (e.g., a handful of residency programs), and it is unclear if they are representative of the entire cohort (i.e., all general surgery residents). Moreover, different study groups analyze existing instruments differently, precluding comparison. (2) Even for the subset of programs that are able to pinpoint specific problems in their learning environments and/or residents’ well-being, there is little to guide them in how to intervene and improve. Few interventions exist, and there is little robust data to support their adoption, particularly outside of the home institutions in which they were developed. Moreover, programs must seek interventions out, generally through word of mouth, as there is no standardized format for sharing with others.

Finally, our qualitative work with residents, faculty, and program directors revealed concerns about the potential negative impact of wellness interventions on training (e.g., more time off may result in less clinical experience). Thus, there is a need to assess the impact of wellness interventions on resident education and training.

## SECTION B

### STUDY OBJECTIVES

---

To transform the learning environment in general surgery residency, we will again partner with the ACGME, ACS, and ABS, along with the Association of Program Directors in Surgery (APDS), Society of Surgical Chairs (SSC), the Association for American Medical Colleges (AAMC), and the Residents and Associates Society of the ACS (RAS-ACS) to conduct the national Surgical Education Culture Optimization through targeted interventions based on National comparative Data (SECOND) Trial. The SECOND Trial is another national, pragmatic, cluster-randomized trial in which enrolled surgical residency programs will be randomized to either a “Control” or a multi-faceted “Intervention” condition.

Each program will receive nationally benchmarked data on residents’ well-being through three specific outcomes: burnout, thoughts of attrition, and suicidal thoughts. “Intervention” programs will additionally receive (1) a Learning Environment Report, containing more granular data (e.g., duty hour violations, autonomy, sexual harassment), (2) a Wellness Toolkit of ready-to-implement interventions, and (3) implementation support, consisting of process improvement coaching, peer mentoring, collaboration networking, and topical experts to assist programs in implementing Toolkit solutions, adapted to their local contexts.

**Objective 1:** To develop a comprehensive, multifaceted Wellness Toolkit of potential interventions to improve the resident learning environment.

**Expected Outcome:** We will undertake four approaches to develop a comprehensive, multifaceted Wellness Toolkit of ready-to-implement interventions: (1) a thorough review of literature and best practice guidelines, (2) a survey-based inventory of wellness initiatives at each program, (3) phone interviews with program directors to gather further information about initiatives reported in the inventory, and, most importantly, (4) two-day Program Tours of representative programs that will provide insight about the various factors (e.g., environmental, infrastructural, and cultural) that impact the learning environment and resident well-being.

**Objective 2:** To assess the impact of the SECOND Trial Intervention (Learning Environment Reports, Wellness Toolkit, implementation support) on (A) resident well-being, (B) resident education, and (C) patient outcomes.

**Expected Outcome:** A pragmatic cluster-randomized trial will demonstrate that access to personalized, nationally-benchmarked data, along with an array of ready-to-implement interventions and implementation assistance, will (A) measurably improve the learning environment and resident well-being without (B) negatively impacting resident education or (C) patient care.

**Objective 3:** To refine the Wellness Toolkit by identifying successful context-specific interventions and expanding intervention access to the Control arm.

**Expected Outcome:** By examining specific initiatives implemented by programs as well as their successes and failures, we will be able to identify (1) particular interventions, (2) groups of interventions, or (3) configurations of interventions that are beneficial in certain contexts (e.g., large, urban programs and small, rural programs have unique needs requiring different interventions). Based on these data, the Wellness Toolkit will be refined, and access will be expanded to all participating residency programs.

## SECTION C

### STUDY ENDPOINTS

#### C.1. PRIMARY ENDPOINT

The primary study endpoint is resident burnout, as measured by the abbreviated Maslach Burnout Inventory, which is incorporated into the SECOND Trial Resident Survey. Power calculations were based upon this endpoint. Details on measurement are in §E1.

#### C.2. SECONDARY ENDPOINTS

C.2.1 Resident Well-Being: Our conceptual model is adapted from Shanafelt's Areas of Work-Life, which posits that organizational performance on various domains impacts clinician well-being. These domains (and their component items) will serve as secondary endpoints in the measurement of resident well-being:

- Workload & Job Demands
- Efficiency & Resources
- Organizational Culture
- Control & Flexibility
- Meaning in Work
- Resident Camaraderie
- Faculty Engagement
- Work-Life Integration

Based upon our 2018 ABSITE Survey data, we also added the following:

- Mistreatment

In 2019, we added a series of questions to address these domains. Confirmatory Factor Analysis was performed on the responses to validate these metrics and their fit within our conceptual model. See **Appendix 1** for Confirmatory Factor Analysis.

C.2.2 Resident Education: The following secondary endpoints will be examined to assess the impact of wellness interventions on resident education:

- ABSITE scores
- ABS Qualifying Examination (QE) scores
- ABS Certifying Examination (CE) scores
- SECOND Trial Resident Survey
- ACGME Case Log data
- ACGME Annual Resident and Faculty Surveys

C.2.3 Patient Outcomes: The following secondary endpoints will be examined to assess the impact of wellness interventions on patient outcomes in the subset of programs that participate in the American College of Surgeons National Surgical Quality Improvement Program (ACS NSQIP):

- 30 day postoperative death or serious morbidity
- 30 day postoperative death
- 30 day postoperative morbidity (NSQIP composite)
- 30-Day Postoperative Surgical Site Infection (SSI)

- 30-Day Postoperative Respiratory Complications (composite of pneumonia, intraoperative or postoperative unplanned intubation, pulmonary embolism, ventilation  $\geq 48$  hours)
- 30-Day Postoperative Pneumonia
- 30-Day Postoperative Urinary Tract Infection
- 30-Day Postoperative Renal Failure
- 30-Day Postoperative Venous Thromboembolism (deep vein thrombosis and/or pulmonary embolism)
- 30-Day Postoperative Stroke
- 30-Day Postoperative Myocardial Infarction
- 30-Day Intra- and Postoperative Transfusion
- 30-Day Postoperative Sepsis/Septic Shock
- 30-Day Postoperative Unplanned Return-to-Operating Room
- 30-Day Postoperative Unplanned Readmission
- Non-Home Discharge
- Failure to Rescue
- 30-Day Postoperative Cardiac Complications (NSQIP composite)

Details on measurement of all secondary outcomes are in §E2.

## **D.1. OVERVIEW**

The SECOND Trial is a two-arm cluster-randomized, pragmatic trial to test the effectiveness of a multi-component intervention to reduce burnout among residents training in accredited general surgery residency programs in the United States.

General surgery residency programs randomized to Control and Intervention arms will receive program-specific feedback reports on 3 basic resident outcomes: burnout, thoughts of attrition, and thoughts of suicide, as well as access to interventions related to suicidality.

General surgery residency programs randomized to Intervention will also receive a multi-component intervention consisting of (1) program-specific feedback on the learning environment and resident well-being, (2) a Wellness Toolkit containing ready-to-implement interventions for improving the learning environment and resident well-being, and (3) implementation support for adapting these interventions to the local context.

### **D.1.1. Justification of Cluster Randomization**

The SECOND Trial is a cluster-randomized trial of general surgery residency programs and their residents to one of two study arms. The unit of randomization is the general surgery residency program. Individual residents will be assigned as a “cluster” to Control or Intervention based on the (random) study assignment of their residency program. This is because program policies and organizational features/structures to improve the learning environment and resident well-being are implemented at the organizational level. Once implemented, such measures are generally non-excludable – i.e. it cannot selectively benefit one resident but not another. Moreover, because some have argued and demonstrated that wellness (particularly suicidality) may be subject to social contagion, it is neither practically feasible nor statistically tenable to randomize individual residents within programs as any change in wellness may spill over and affect those in the same program regardless of study arm assignment under conditions of individual randomization.

### **D.1.2. Justification of Pragmatic Nature**

The SECOND Trial is a pragmatic trial because programs will be offered feedback and strategies for improving the learning environment and resident well-being, but there will be no mandate by the Investigators to force Intervention programs to consider and/or act upon their feedback or prevent Control programs from acting upon theirs. Programs may attempt to improve their program measures at will, regardless of study arm. The only thing that distinguishes the Intervention from the Control Arm is the receipt of granular information on the learning environment, access to the Wellness Toolkit, and implementation support in the Intervention Arm.

## **D.2. INSTITUTIONAL REVIEW BOARD ASSURANCES**

The ABSITE Survey protocol was reviewed by the Northwestern University IRB (NU IRB) as part of the FIRST Trial protocol and determined to be exempt from further review (IRB #STU00208523).

The Program Wellness Initiatives Inventory Survey protocol was reviewed by the NU IRB and approval was expedited (IRB #STU00209204).

The Program Tours component of the study protocol was reviewed by the NU IRB and approval was expedited (IRB #STU00208859).

The SECOND Trial protocol was reviewed by the NU IRB and deemed to be non-human subjects research and thus exempt from further review (IRB #STU00209709).

See **Appendix 2** for facsimiles of IRB documentation pertaining to the SECOND Trial.

Residency programs may elect to submit IRB applications to their local IRBs. Given that the trial itself was deemed to be non-human subjects research, NU IRB will not act as the IRB of record for external sites.

### **D.3. STUDY POPULATION**

The study population for the SECOND Trial includes all general surgery residency programs in the United States that were accredited by the Accreditation Council for Graduate Medical Education (ACGME) as of April 2019.

## **D.4. STUDY ELIGIBILITY CRITERIA**

### **D.4.1. Study Inclusion Criteria**

Residency programs were eligible to enroll/participate in the SECOND Trial if they met the following study inclusion criteria:

- The residency program was in General Surgery.
- The residency program was ACGME-approved as of April 2019.

### **D.4.2. Study Exclusion Criteria**

Residency programs were ineligible for participation in the SECOND Trial if they met the following exclusion criteria:

- The residency program was not in General Surgery.

## **D.5. RECRUITMENT AND ENROLLMENT**

This section provides an overview of the procedures used to recruit eligible general surgery residency programs (see §D.4) into the SECOND Trial.

### **D.5.1. Sampling Frame**

A list of all ACGME-approved General Surgery residency programs was provided by the ACGME. This list served as our “sampling frame.”

### **D.5.2. Initial Contact**

An initial contact email was sent to the program directors of all residency programs in the sampling frame. The initial contact email (1) provided a descriptive overview of the SECOND Trial, including key objectives of the study and answers to frequently asked questions, (2) invited them to attend one of two informational webinars and/or an in-person Town Hall meeting at the annual Association of Program Directors in Surgery (APDS) meeting. In both the webinars and the Town Hall meeting, additional details about the SECOND Trial were shared and opportunities to ask questions and/or give feedback were given. The initial contact email was signed by the co-Principal Investigators ([name], [name]) and leadership from the ACS and APDS.

### **D.5.3. Informational Outreach**

Two one-hour long informational webinars were conducted over the internet on April 4, 2019 and April 10, 2019. One one-hour long Town Hall meeting was conducted during the annual Association of Program Directors in Surgery meeting on April 2019. The informational webinars and the Town Hall meeting were led by the Principal Investigators. Attendees included one or more of the following representatives from the residency programs in our target sample: residency program directors and coordinators; leaders of surgical departments; educational and/or wellness leaders in surgical residency programs. The following content was covered:

- Study motivation
- Study objectives
- General design and endpoints
- Study eligibility
- Recruitment/enrollment
- Randomization
- Study arm descriptions – i.e., what participation entails
- Data collection
- Study timeline
- IRB exemption/approval
- Institutional endorsement/support – i.e., ACGME, ACS, ABS, APDS, Society of Surgical Chairs (SSC), the Association for American Medical Colleges (AAMC), and the Residents and Associates Society of the ACS (RAS-ACS)
- Question and answer
- Next steps

#### D.5.4. Enrollment Forms

On June 26, 2019, an enrollment email was sent to department chairs, program directors, program coordinators, and designated institutional officials at each program in our sampling frame. This email summarized the information that was presented during the informational webinars and Town Hall meeting, requested basic information about the residency programs, enumerated terms of participation, and requested signatures from the department chairs, program directors, and designated institutional officials. Programs were given until August 30 to remit completed enrollment forms. The deadline was then extended to October 31, 2019, given the considerable interest from programs who needed more time.

Terms of participation for all eligible residency programs were as follows:

- Agree to randomization to one of the two study arms
- Agree that if randomized to the intervention arm, it is entirely up to the program leadership to decide which, if any, interventions to implement
- Agree that their Program Director will participate in an initial brief phone call with the study team to learn about their program, if requested
- Agree that their Program Director will participate in a brief annual survey in order to establish which wellness interventions are underway or have been initiated at their program. (As was done for the FIRST Trial)
- As the reports provided by the SECOND Trial are for internal evaluation to improve wellness, agree not to advertise data any of the data provided by the SECOND Trial regarding resident wellness (e.g., burnout, attrition) in any public forum, including, but not limited to, social media, program website, resident recruitment/interview materials, and resident recruitment day activities
- Agree to not share access or content of Wellness Toolkit with other residency programs during the course of the Trial. All participating programs will receive the Toolkit at the end of the study
- Acknowledge that their residents will complete a brief survey annually for the SECOND Trial (As was done for the FIRST Trial)
- Agree that the American Board of Surgery (ABS) can share de-identified data with the SECOND Trial Coordinating Center, including (1) American Board of Surgery In-Training Examination (ABSITE) and (2) ABS written Qualifying Examination and oral Certifying Examination scores and pass rates (As was done for the FIRST Trial)
- Agree the Accreditation Council of Graduate Medical Education (ACGME) can share electronic data for years 2014-2024 with the SECOND Trial Coordinating Center, including (1) Annual Resident Survey data aggregated at program level (no individual identifiers); (2) Annual Faculty Survey data aggregated at program level (no individual identifiers); (3) Case Log de-identified, individual-level data (i.e., to examine resident case volumes for the surgical defined categories) with program identifiers; (4) any general descriptive information on programs (e.g., size, geography); (5) de-identified individual-level data on residents who did not graduate from their programs (e.g., demographics, year of departure, PGY level, and reasons for leaving if available) with program identifiers; (6) contact information for Program Director(s), Program Coordinator(s), Designated Institutional Official, and Chair for each program; and (8) other relevant program-level data that may be beneficial for the SECOND Trial. Programs will be identified via ACGME program identifier and no ACGME data will be transmitted if there are less than four responses per program per survey in any given year or the programs failed to meet the minimum compliance rate
- Agree to allow the American College of Surgeons National Surgical Quality Improvement Program (ACS NSQIP) to share de-identified data with the SECOND Trial Coordinating Center (As was done for the FIRST Trial)

- Agree to allow the Association of American Medical Colleges (AAMC) to share de-identified data with the SECOND Trial Coordinating Center, including (1) medical school graduate survey; (2) resident, faculty, leadership characteristics/demographics; and (3) other relevant program-level data that may be beneficial for the SECOND Trial

In 2020, an addendum to the agreement between ACS NSQIP and the hospital will be signed by each willing participating hospital. This addendum will allow transfer of ACS NSQIP data to the study team at Northwestern.

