### **D.7.3. Randomization Procedure and Treatment Assignment**

General surgery residency programs that enroll in the SECOND Trial will be grouped into four strata:

- Stratum 1 – Quartile 1, 2019 ABSITE program mean resident burnout scores
- Stratum 2 – Quartile 2, 2019 ABSITE program mean resident burnout scores
- Stratum 3 – Quartile 3, 2019 ABSITE program mean resident burnout scores
- Stratum 4 – Quartile 4, 2019 ABSITE program mean resident burnout scores
- Stratum 5 – *No data* on 2019 ABSITE program mean resident burnout score

Residency programs within each stratum will be assigned a unique, randomly-generated integer using a random-number generator. Residency programs within each stratum will be ordered in ascending order according to their randomly-assigned number. Four separate, blinded lists will be constructed containing the randomly-generated numbers corresponding to each program within each of the four strata. These blinded lists will be given to the Project Coordinator, who, with another Study Team member to be appointed, will alternately assign programs to Control or to Intervention. They will decide to start with control or intervention on the basis of a coin toss. An observer unaffiliated with the study will be present.

Once study arm assignments have been made for each of the four blinded lists, the blinded lists will then be sent back to the Statistical Analyst who will then unblind the lists. Final, unblinded residency program study arm assignments will be sent back to the Project Coordinator, so that participating programs may be notified of their study arm assignment. Study arm assignments will not be made public, but programs participating in the trial will be listed on the SECOND Trial website and [www.clinicaltrials.gov](http://www.clinicaltrials.gov).

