#### D.9. STUDY SAMPLE

A total of 209 residency programs enrolled in the SECOND Trial.

Exhibit D.9 shows the distribution of SECOND Trial residency program participants as of November 8, 2019.

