**Exhibit D.9. SECOND Trial Sample as of November 8, 2019**

UNIT	Control N	Intervention N	Total N
General Surgery Residency Programs	106	103	209
Mean Burnout T-score a (SD)	50.48 (3.07)	49.98 (3.88)	-
Program Type			
Academic	55	52	107
Community	46	48	94
Military	3	2	5
Mean Number of Residents (SD)	34.08 (16.77)	33.88 (15.95)	-

NOTE: [a] Based on 2019 ABSITE data.

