### **D. 11.5. ACS NSQIP Data**

The hospital of primarily affiliated with the enrolled residency programs will be asked in 2020 to grant the Study Team access to their hospitals' ACS NSQIP data.

A detailed, official description of the ACS NSQIP data can be found here:  
<http://site.acsnsqip.org/participant-use-data-file/>

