#### ***F.3.2.2. Secondary Patient Outcomes***

As discussed in §C.2.3, we will evaluate the effect of program participation in Intervention on various postoperative outcomes of patients undergoing surgery in hospitals associated with those programs compared to patients in hospitals associated with programs that did not participate in the Intervention. This evaluation will only be carried out among programs associated with hospitals that participate in the ACS NSQIP program.

Patient outcomes are dichotomous variables indicating whether a patient experienced each of the following postoperative complications:

- 30 day postoperative death or serious morbidity
- 30 day postoperative death
- 30 day postoperative morbidity (NSQIP composite)
- 30-Day Postoperative Surgical Site Infection (SSI)
- 30-Day Postoperative Respiratory Complications (composite of pneumonia, intraoperative or postoperative unplanned intubation, pulmonary embolism, ventilation  $\geq 48$  hours)
- 30-Day Postoperative Pneumonia
- 30-Day Postoperative Urinary Tract Infection
- 30-Day Postoperative Renal Failure
- 30-Day Postoperative Venous Thromboembolism (deep vein thrombosis and/or pulmonary embolism)
- 30-Day Postoperative Stroke
- 30-Day Postoperative Myocardial Infarction
- 30-Day Intra- and Postoperative Transfusion
- 30-Day Postoperative Sepsis/Septic Shock
- 30-Day Postoperative Unplanned Return-to-Operating Room
- 30-Day Postoperative Unplanned Readmission
- Non-Home Discharge
- Failure to Rescue
- 30-Day Postoperative Cardiac Complications

Each outcome will be modeled separately using hierarchical logistic regression models of the general form

$$\log \left( \frac{Pr(\text{complication}_{ijk} = 1 | TREAT_{ijk}, x, z, \zeta_j^{(2)}, \zeta_r^{(3)})}{(1 - (Pr(\text{complication}_{ijk} = 1 | TREAT_{ijk}, x, z, \zeta_j^{(2)}, \zeta_r^{(3)})))} \right) =$$

$$\beta_0 TREAT_j + \beta_1 x_{1ijr} + \beta_2 x_{2ijr} + \cdots + \beta_k x_{kijr} + \gamma_1 z_{1jr} + \cdots + \gamma_m z_{mjr} + \zeta_j^{(2)} + \zeta_r^{(3)}$$

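### Hospitals release NSQIP data voluntarily in 2020, after randomisation, so the patient-outcome set can be selected after allocation, and the SAP makes no provision for this

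*SAP*

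**What the plan says.** Section D.5.4 lists the terms that programs accepted on the 2019 enrolment form, and agreement to NSQIP data sharing is one of them. It then adds a separate step at hospital level: "In 2020, an addendum to the agreement between ACS NSQIP and the hospital will be signed by each willing participating hospital". The purpose of that step is stated: "This addendum will allow transfer of ACS NSQIP data to the study team at Northwestern". Section D.11.5 gives the same timing; the hospital primarily affiliated with each program "will be asked in 2020 to grant the Study Team access to their hospitals' ACS NSQIP data".

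Allocation comes earlier. Exhibit D.9 shows 106 Control and 103 Intervention programs under the title "SECOND Trial Sample as of November 8, 2019". Section D.7.3 says the unblinded assignments are returned "so that participating programs may be notified of their study arm assignment". The Section H timeline places randomisation in November 2019, program reports in December 2019 and Toolkit delivery to Intervention in January 2020.

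The analysis set is described only by NSQIP status in F.3.2.2: "This evaluation will only be carried out among programs associated with hospitals that participate in the ACS NSQIP program". Section C.2.3 uses the same definition.

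**The concern.** NSQIP participation could be fixed before randomisation. Signing the addendum cannot be, on the SAP's own schedule. If the tendency of better or worse hospitals to sign differs between arms, the signers in the two arms are no longer comparable at baseline, and an odds ratio away from 1 can arise with no true effect.

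Objective 2C is the trial's check that wellness changes do not harm patient care, so a modest shift in either direction matters to how that conclusion is read. The SAP does not say how NSQIP hospitals that decline are handled. It plans no count of release by arm and no comparison of signers across arms. Section E.6 deals with incomplete observations and survey imputation, not with whole hospitals that supply nothing. Section G does not list the issue.

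**Working it through.** **Order of events**

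| Step | Date | Source |
|---|---|---|
| Enrolment closes, NSQIP sharing agreed by program | October 31, 2019 (D.5.4, D.5.6) or 9.30.19 (Section H) | D.5.4, D.5.6, H |
| Randomisation; arm counts shown | 11.2019; as of November 8, 2019 | H, Exhibit D.9 |
| Program reports | 12.2019 | H |
| Toolkit to Intervention | 1.2020 | H |
| Hospital addendum | 2020, no month | D.5.4, D.11.5 |

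The arm counts add up: 106 + 103 = 209. The two enrolment closing dates differ, but both precede randomisation. Even an addendum signed on the first day of 2020 follows allocation.

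**Possible size**

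The SAP gives no expected number of signing hospitals, no margin and no power for patient outcomes, so there is no figure of its own to reproduce. The inputs below are assumptions.

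- SD of the hospital log-odds of death or serious morbidity: 0.25.
- Correlation rho between better outcomes and signing: 0.2 to 0.5.
- Share signing in an arm: p.

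Under a normal selection model, the mean log-odds among signers falls by rho × SD × m(p), where m(p) = phi(z_p)/p. The values are m(0.5) = 0.798, m(0.6) = 0.644, m(0.7) = 0.497, m(0.8) = 0.350 and m(0.9) = 0.195.

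With the same rho in both arms and no true effect, the odds ratio for Intervention against Control is exp(rho × SD × [m(p_Control) − m(p_Intervention)]).

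- Signing 80% Intervention, 60% Control, rho 0.3: 0.3 × 0.25 × (0.644 − 0.350) = 0.022, odds ratio 1.02.
- Signing 90% Intervention, 50% Control, rho 0.5: 0.5 × 0.25 × (0.798 − 0.195) = 0.075, odds ratio 1.08.

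If signing depends on quality in one arm only, the shift is rho × SD × m(p) even with equal signing rates.

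- p = 0.7, rho 0.2: 0.2 × 0.25 × 0.497 = 0.025, odds ratio 1.03 if Control selects, 0.98 if Intervention selects.
- p = 0.5, rho 0.3: 0.3 × 0.25 × 0.798 = 0.060, odds ratio 1.06 if Control selects, 0.94 if Intervention selects.

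With rho = 0, or the same rho and the same p in both arms, the shift is zero.

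**The case against.** The strongest answer is the enrolment form. Before randomisation, the chair, program director and designated institutional official were asked to sign terms that include NSQIP sharing. Refusing in 2020 because of the arm would go against an agreement already given. This lowers the risk and belongs in any account of it. It does not remove the risk, because the SAP still makes transfer depend on a separate signature from a willing hospital.

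Knowledge of the arm is also an inference. Programs are notified, but the signatory is the hospital, arm assignments are not made public, and no passage dates the notification or says that the signatory is told. Toolkit delivery in January 2020 means that Intervention programs know their arm by then; it does not show what the hospital signatory knows.

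Planned adjustment would absorb part of any selection. F.3.2.2 uses outcome-specific NSQIP risk models and hospital-level covariates, and F.3.3.1 allows analyses that take baseline rates into account. The pre-post analyses are optional, and the baseline-quality measure appears in E.4 only among measures that may be used. The SD of 0.25 is not reduced for adjustment, so the shifts above are on the high side for an adjusted model.

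Three stronger readings are tempting, and the documents support none of them.

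- A reader might infer that randomisation no longer protects this comparison. That would follow only if signing is related to outcome differently by arm, which nothing in the SAP shows.
- A reader might infer that the selection would hide harm. The mechanism that comes first to mind, weaker Control hospitals declining, makes Control look better and pushes the odds ratio above 1, which works against the intervention. The opposite direction is arithmetically possible, but the documents give no reason to expect it.
- A reader might take F.3.2.2's wording about participation in the Intervention as a departure from intent-to-treat. F.3.1.1 and F.3.1.2 define the treatment term as arm assignment and F.1.1 fixes analysis as assigned, so this is an editorial alignment only.

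**Conclusion.** The concern holds in a limited form. Release of NSQIP data is voluntary and follows randomisation, and the set that yields patient outcomes is narrower than the set F.3.2.2 describes. The SAP leaves room for selection after allocation and has no means of detecting it. Whether selection occurred cannot be told from the document.

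Under the assumed inputs, unequal selection would shift the odds ratio by about 2% to 8%, in either direction depending on the arm that selects more. The SAP states no margin against which to call that large or small. The burnout primary endpoint is untouched. This should be repaired, but it does not put the trial's main conclusion in doubt.

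**What to change.** In D.11.5 and F.3.2.2:

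1. Define the eligible set as enrolled programs whose primary hospital was an NSQIP participant before randomisation.
2. Where addenda are still outstanding, send the same request to all of these hospitals with one closing date.
3. Report hospitals eligible, asked and signed by arm, and compare signers across arms on pre-randomisation NSQIP outcomes.
4. Make the death or serious morbidity baseline-quality measure listed in E.4, computed on pre-randomisation cases, a required covariate in the patient-outcome models.
5. State the post-randomisation release as a limitation in Section G.

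As an editorial matter, word F.3.2.2 in terms of assignment to match F.1.1.

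The cost is SAP wording, one table by arm and a covariate already on the list, provided that the transferred data reach back before November 2019. Items 1, 3, 4 and 5 can be done even if every addendum is already signed. The downside is that the no-harm claim for patients may have to be stated more cautiously.
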